1.5.3 SUBJECTS NOT ANALYZED

An additional cohort (Cohort 4) was planned to explore the safety and tolerability of treating multiple lesions during the same visit; however, no patients were enrolled in Cohort 4.

In addition, multi-lesional PVSRIPO retreatment of patients originally enrolled in Cohorts 0 through 3 was allowed; however, no patients from Cohorts 0 through 3 were retreated with PVSRIPO.

1.6 STATISTICAL METHODS

This section describes the statistical methods addressing the primary and exploratory objectives.

1.6.1 STATISTICAL METHODS FOR SAFETY ANALYSES

Safety and tolerability will be assessed by review of all relevant parameters including AEs, laboratory tests, and vital signs. Summary statistics (eg, counts, percentage, mean, standard deviation) will be provided for the safety endpoints as appropriate. The 95% CI for the incidence rate of injection site reactions and the incidence rate of Grade 3 or 4 AEs will be provided as appropriate.

Adverse Events

AEs will be coded using Medical Dictionary for Regulatory Activities (MedDRA[®]) Version 23.1, with each verbatim term coded to a lowest level term (LLT), which is mapped to a preferred term (PT), high level term (HLT), and a system organ class (SOC).

AE summaries will include only TEAEs, which are defined as AEs that are not present prior to the start of study medication, or AEs present before study medication that worsened after starting study medication. If a partially missing date or time of onset allows the possibility that an AE may be a TEAE, it will be assumed the event is a TEAE.

An overall summary of the number and percentage of subjects in each category will be presented, as well as an overall summary of the number of events in each category.

The Investigator will provide an assessment of the severity of each AE using CTCAE Version 4.0.

Note: “Severe” is a measure of intensity; it is not equivalent to “serious”. Subjects will be counted and summarized under their highest severity within a SOC and PT.

If the relationship between the AE or serious adverse event (SAE) and the investigational product is determined to be possibly, probably, or definitely related, the event will be considered as related to the investigational product for the purposes of reporting. Otherwise, the AE or SAE will be considered ‘unrelated.’

Each subject will be counted once within each preferred term. If a subject experienced more than one TEAE within a preferred term only the TEAE with the strongest relationship or the maximum intensity, as appropriate, will be included in the summaries of relationship and intensity. No inferential statistical tests will be performed.

For TEAE’s, summary tables showing the incidence rates (frequencies and percentages) and number of events for the following categories will be prepared:

- Overall Summary of TEAEs
- TEAEs by SOC and PT
- TEAEs by PT in descending frequency
- PVSRIPO-Related TEAEs by SOC and PT
- PVSRIPO-Related TEAEs by PT in descending frequency
- Severe (Grade 3), Life Threatening (Grade 4) and Fatal (Grade 5) TEAEs by SOC and PT
- Severe (Grade 3), Life Threatening (Grade 4) and Fatal (Grade 5) PVSRIPO-Related TEAEs by SOC and PT
- Listing of SAEs
- Listing of DLTs

Definition of Dose Limiting Toxicities

For Cohorts 0 through 3, DLTs were identified from the time of each PVSRIPO injection until the end of a 21-day observation period following each injection. DLTs were defined as any of the below events that did not resolve to pre-treatment baseline or \leq Grade 1 within 21 days or any toxicity indicated below that resolved within the 21-day period, but then recurred as Grade 4 or higher during that same 21-day period.

DLTs include:

- Any Grade 4 or higher non-hematologic toxicities probably, possibly, or definitely related to PVSRIPO, with the exception of vitiligo
- Any Grade 4 or higher hematologic toxicities probably, possibly, or definitely related to PVSRIPO.

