1.4.1 SAFETY ENDPOINTS

Adverse events will be graded using National Cancer Institute (NCI) Common Terminology Criteria for Adverse Events (CTCAE) v4.0. The primary safety endpoint for this Phase 1 study is the proportion of subjects experiencing a DLT within each cohort. An adverse event (AE) is considered a DLT, if it meets the following criteria:

- Grade 4 or higher non-hematologic treatment-related adverse event (TEAE), with the exception of vitiligo.
- Grade 4 or higher hematologic TEAE

Additional safety endpoints include assessment of all TEAEs experienced by subjects who received at least one intratumoral injection of PVSRIPO, laboratory safety assessments, vital signs, reasons for treatment discontinuation, and physical examinations.

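### SAP 1.6.1 reports an adverse event with missing causality as unrelated, which can understate the PVSRIPO-related TEAE tables

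*SAP*

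**What the plan says.** SAP 1.6.1 turns the investigator's causality assessment into two reporting classes. The related class needs a positive determination: "If the relationship between the AE or serious adverse event (SAE) and the investigational product is determined to be possibly, probably, or definitely related". Everything else goes the other way: "Otherwise, the AE or SAE will be considered" unrelated. The sentence limits this split to reporting.

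The same section has one explicit missing-data rule for adverse events. When a partly missing onset date or time leaves open that the event began after dosing, "it will be assumed the event is a TEAE".

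Protocol 12.1 collects attribution on five levels: definite, probable, possible, unlikely and unrelated. There is no level for missing or unknown. Protocol 13.3.2 sends missing data to the PI, but accepts as one possible reply a confirmation that the value cannot be supplied. Neither document says how an event without a causality assessment is then classed.

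On DLTs, SAP 1.4.1 states: "The primary safety endpoint for this Phase 1 study is the proportion of subjects experiencing a DLT within each cohort". SAP 1.6.1 and Protocol 8.1.3 both make relatedness part of the DLT definition, for example "Any Grade 4 or higher hematologic toxicities probably, possibly, or definitely related to PVSRIPO". SAP 1.4.1 words it differently: "Grade 4 or higher non-hematologic treatment-related adverse event (TEAE), with the exception of vitiligo". Its hematologic bullet refers only to a TEAE, and SAP 1.6.1 defines that term by timing alone: "AE summaries will include only TEAEs, which are defined as AEs that are not present prior to the start of study medication".

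**The concern.** The complement of the three related categories is wider than the scale's two remaining levels, unlikely and unrelated. It also takes in an event for which nothing was determined. In an open-label, single-arm study whose purpose is safety, the usual convention is that missing causality counts against the product until shown otherwise. Here the wording does the opposite.

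This also departs from the SAP's handling of other uncertain data. A doubtful onset date makes an event treatment-emergent. A subject with several events under one preferred term is counted at the strongest relationship. A subject without response data is a non-responder (SAP 1.6.2). Each of these resolves doubt against the product.

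At stake are the tables restricted to PVSRIPO-related TEAEs: by SOC and PT, by PT in descending frequency, and the Grade 3 to 5 version. With 12 subjects, a single misclassified subject is visible in a percentage.

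**Working it through.** **1. Denominator.** SAP 1.1 gives 4 cohorts of 3 subjects: 4 × 3 = 12, which reproduces the stated total. The sample size is not formula-based, so there is no power figure to reproduce.

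**2. Where each recorded value goes.**

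| Causality at lock | SAP 1.6.1 as written | With the proposed sentence |
|---|---|---|
| Definite, probable, possible | related | related |
| Unlikely, unrelated | unrelated | unrelated |
| Missing after query | unrelated (by the catch-all) | related, listed separately |

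Only the last row differs.

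**3. Size in the related-TEAE tables.** One subject moved from unrelated to related changes a rate by 1/12 = 8.3 percentage points overall, and by 1/3 = 33.3 points within a cohort if the table is split by cohort, as Protocol 14.4 foresees for toxicities. Because SAP 1.6.1 counts a subject once per preferred term at the strongest relationship, the subject-level rate for a term moves only if that subject has no other related event under it. The count of related events moves in either case.

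**4. Which tables can change on the reported data.** Protocol 6.2.4, 8.1.5 and 8.7 report, for the 12 patients in Cohorts 0 to 3, no DLT, no SAE and no event above Grade 2. SAP 1.5.3 says that nobody entered Cohort 4 or was retreated.
- DLTs: a DLT needs Grade 4 or higher. No such event is reported, so the count is 0/12 under either classification.
- Related Grade 3 to 5 TEAEs: no event of these grades is reported, so the table is the same under either classification.
- Related TEAEs of any grade: Grade 1 and 2 events are included, so these tables can change.

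**5. A hypothetical Grade 4 event, for scale only.** The SAP does not name the interval method for DLTs; I assume the exact (Clopper-Pearson) method. For x = 0 the upper 95% limit is 1 − 0.025^(1/n). For x = 1 the lower limit is 1 − 0.975^(1/n), and the upper limit is the 0.975 quantile of Beta(2, n − 1).

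| DLTs | Rate | Exact 95% CI |
|---|---|---|
| 0/3 | 0% | 0 to 70.8% |
| 1/3 | 33.3% | 0.8 to 90.6% |
| 0/12 | 0% | 0 to 26.5% |
| 1/12 | 8.3% | 0.2 to 38.5% |

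Step 4 shows that the reported data contain no event to which this applies.

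**The case against.** The sentence can be read as a plain reduction of a five-level scale to two classes, with the catch-all meant for unlikely and unrelated. On that reading the SAP has no rule for missing causality at all, and calling it one is an inference. This is fair as to intent. It does not change the result: a programmer applying the sentence to an empty field would report the event as unrelated.

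Missing causality should also be rare. Protocol 12.1 expects an attribution for adverse events, Protocol 12.1.2 categorises each event by relationship, and Protocol 13.3.2 has automatic completeness checks and closes the database only once queries are resolved. In a single-site study of 12 patients the number left may well be zero. This stands and limits the practical weight of the point. It does not close the gap, because the query process itself allows a reply that the value is unavailable.

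Nor would a serious event be hidden. The SAP plans all-causality TEAE tables, an all-causality Grade 3 to 5 table, an SAE listing and a confidence interval for Grade 3 or 4 events. This also stands: the possible distortion is confined to the tables restricted to related events.

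**Conclusion.** The point holds as an inexpensive improvement to the reporting rule. As written, SAP 1.6.1 resolves missing causality in the product's favour, against its own handling of partly missing onset dates. The exposure is the PVSRIPO-related TEAE tables, at 8.3 percentage points per subject in 12, for an unknown and possibly zero number of events.

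A reader might go further and infer that an event with missing causality cannot be a DLT, so that this sentence biases the primary endpoint. The documents do not support that, for four reasons.
- The default applies to reporting. The SAP describes DLTs, in the past tense, as identified over the 21 days after each injection.
- The relatedness requirement comes from the DLT definition itself, in Protocol 8.1.3 and SAP 1.6.1. Deleting the default would leave it unchanged.
- SAP 1.4.1 is ambiguous. If TEAE there means treatment-emergent, as SAP 1.6.1 defines it, an event with missing causality could count as a DLT.
- On the reported data the DLT count is 0/12 either way.

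The conclusion assumes that the severity data, which the protocol gives as of its amendment of 29 May 2020, still hold at database lock. Enrollment and PVSRIPO treatment in Cohorts 0 to 3 were complete by that amendment.

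**What to change.** Replace the catch-all sentence in SAP 1.6.1 with: *Events assessed as unlikely or unrelated are reported as unrelated. Missing relationship is queried before database lock; if still missing, the event is counted as related in the related-TEAE summaries and listed separately.*

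Flag any Grade 4 or higher event with missing causality beside the DLT listing. Do not alter the DLT definition to absorb it: that definition governed escalation, and dosing has ended.

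Reconcile the DLT wording in SAP 1.4.1 with that in SAP 1.6.1, so that treatment-related and treatment-emergent do not share one abbreviation and the two sections cannot class the same event differently.

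The cost is a few lines of SAP text and a pre-lock check of one field. If no causality entry is missing, no table changes. If some are, related-event rates may become slightly less favourable, and the separate listing shows by how much.

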1.6.2 STATISTICAL METHODS FOR EXPLORATORY EFFICACY ANALYSES

Efficacy will be evaluated in the FAS population. For the key efficacy endpoint of ORR based on irRC, the point estimate, and 95% CI (as determined by the upper and lower 97.5% one-sided

confidence bounds) will be provided using an exact binomial distribution. Subjects without response data will be counted as non-responders.

DOT will be summarized using Kaplan-Meier (KM) method in all responders.

An outline of the key efficacy analysis strategy is presented in Table 1.

Table 1 Primary Analysis Strategy for Efficacy Endpoints

Endpoint/Variable (Description, Time Point)	Statistical Method	Analysis Population	Missing Data Approach
Primary:			
Overall irRC response rate based on investigator assessment	Exact test of binomial parameter	FAS	Subjects with missing data are considered non-responders
Secondary:			
Overall RECIST 1.1 response rate based on investigator assessment	Exact methods for binomial parameter	FAS	Subjects with missing data are considered non-responders
Response duration (RECIST 1.1)	Summary statistics using Kaplan-Meier method	All responders	Non-responders are excluded in analysis
Response duration (irRC)	Summary statistics using Kaplan-Meier method	All responders	Non-responders are excluded in analysis
Exploratory:			
Overall irRC response rate and RECIST 1.1 response rate based on investigator assessment without requiring confirmatory scans for (ir)CR/PR responses	Exact methods for binomial parameter	FAS	Subjects with missing data are considered non-responders

CR = complete response; FAS = full analysis set; ir = immune related; irRC = immune-related response criteria; PR = partial response; RECIST = response evaluation criteria in solid tumors

Details of the exploratory biomarker analysis strategy will be documented in the sSAP.

1.6.3 DEMOGRAPHIC AND BASELINE CHARACTERISTICS

Baseline characteristics will be assessed using tables and/or graphs. No statistical hypothesis tests will be performed on these characteristics. The number and percentage of subjects screened, enrolled, primary reasons for screening failure, and discontinuation will be displayed. Demographic variables (eg, age, sex), baseline characteristics, primary and secondary diagnoses, and prior and concomitant therapies will be summarized either by descriptive statistics or categorical tables as appropriate.

1.7 MULTIPLICITY

The main efficacy objective of ORR per irRC in the FAS Population will be assessed by a point estimate and 95% CI. There are no formal hypotheses, and no adjustments for multiplicity will be applied. Evaluation of objectives should be interpreted with caution due to the potential for an increase in the false positive rate.

1.8 SAMPLE SIZE AND POWER CALCULATIONS

Given the purpose of this study was to determine the recommended dose and dosing regimen of PVSRIPO in anti-PD-1 resistant melanoma, the sample size was chosen to characterize the safety and initial anti-tumor activity of PVSRIPO. The sample size is not based on statistical considerations; therefore, no inference will be drawn from any statistical tests conducted.

1.9 RESPONSE CRITERIA

1.9.1 IMMUNE RELATED RESPONSE CRITERIA

For all patients who experience disease progression on study, the date noted for disease progression is the time of the scan where it is originally detected, and not the following date of the confirmatory scan. If a scan was not available, the date of disease progression was identified by the Investigator.

Definitions of measurable and non-measurable disease

Measurable disease: Neoplastic masses that can be precisely measured in 2 in-plane perpendicular diameters. Both the longest diameter and the longest perpendicular must be greater than or equal to 10 mm or 2 times the axial slice thickness, whichever is greater. Lymph nodes must have a short-axis line-length of ≥ 15 mm. Malignant lymph nodes must be measurable in 2 perpendicular diameters. Both the longest diameter and the longest perpendicular must be greater than or equal to 15 mm or 2 times the axial slice thickness. The quantitative endpoint will be defined as the product of the longest diameter with its longest perpendicular.

Non-measurable disease: Non-measurable lesions are those that are not suitable for quantitative assessment over time. These include:

1. Neoplastic masses that are too small to measure, because their longest uninterrupted diameter or longest perpendicular are less than 10 mm or two (2) times the axial slice thickness.
2. Neoplastic masses whose boundaries cannot be distinguished. This includes masses that cannot be demarcated from surrounding tissue because of inadequate contrast, masses with overly complex morphology, or those with highly heterogeneous tissue composition.
3. Other types of lesions that are confidently felt to represent neoplastic tissue but difficult to quantify in a reproducible manner. These include bone metastases, leptomeningeal metastases, malignant ascites, pleural/pericardial effusions, inflammatory breast disease, lymphangitis cutis/pulmonis, cystic lesions, ill-defined abdominal masses, etc.

For irRC, only target lesions selected at baseline and measurable new lesions are taken into account.

At the baseline tumor assessment, the sum of the products of the two largest perpendicular diameters (SPD) of all **index lesions** (5 lesions per organ, up to 10 visceral lesions and 5

cutaneous index lesions) is calculated.

At each subsequent tumor assessment, the SPD of the index lesions and of new, measurable lesions ($\geq 5 \times 5$ mm; up to 5 new lesions per organ: 5 new cutaneous lesions and 10 visceral lesions) are added together to provide the total time-point **tumor burden**.

Overall response using irRC:

- Complete Response (irCR): Complete disappearance of all tumor lesions (whether measurable or not, and no new lesions). CR must be confirmed by repeated, consecutive assessments made no less than 4 weeks from the date first documented.
- Partial Response (irPR): $\geq 50\%$ decrease in tumor burden compared with baseline in two observations at least 4 weeks apart.
- Stable Disease (irSD): Failure to meet criteria for irCR or irPR, in absence of irPD.
- Progressive Disease (irPD): At least 25% increase in SPD relative to nadir (minimum recorded tumor burden) Confirmation by a repeat, consecutive assessment no less than 4 weeks from the data first documented.
- Non-index lesions contribute to defining irCR (complete disappearance required).

Immune-related response criteria for the current protocol was adopted from [Wolchok et al, 2009](#).

1.9.2 RESPONSE EVALUATION CRITERIA IN SOLID TUMORS (RECIST) 1.1

RECIST version 1.1 will be used in this study for assessment of tumor response (Eisenhauer et al, 2009).

1.9.3 ADDITIONAL EXPLORATORY RESPONSE EVALUATION CRITERIA

Because of the exploratory nature of the study, some subjects may not have had confirmatory scans prior to exposure to subsequent anti-cancer therapies. Therefore, both irRC and RECIST version 1.1 will be applied without the requirement for confirmatory scans for irCR/irPR and for CR/PR for irRC and RECIST version 1.1, respectively.

Summary statistics comparing the 2 methods of response criteria application (confirmed vs. unconfirmed response) may be calculated for qualitative comparisons.

